9.4.4. Laboratory Tests

For each patient, laboratory tests detailed in (Appendix 2) should be conducted according to the Schedule of Activities (Section 2).

With the exception of laboratory test results that may unblind the study, Lilly or its designee will provide the investigator with the results of laboratory tests analyzed by a central vendor, if a central vendor is used for the clinical trial.

Any clinically significant findings from laboratory tests that result in a diagnosis and that occur after the patient receives the first dose of investigational product should be reported to Lilly or its designee as an AE via eCRF.

9.4.5. Chest x-Ray and Tuberculosis Testing

A posterior anterior view chest x ray will be obtained locally at screening (Visit 1), unless results from a chest x-ray obtained within 6 months prior to the study are available. The chest x-ray will be reviewed by the investigator or his or her designee to exclude patients with active TB infection. In addition, patients will be tested at screening (Visit 1) for evidence of active or latent TB as described in the exclusion criteria, Section 6.2.

9.4.6. Quick Inventory of Depressive Symptomatology Self-Rated–16

The Quick Inventory of Depressive Symptomatology Self-Rated–16 (QIDS-SR₁₆) is a 16-item, self-report instrument intended to assess the existence and severity of symptoms of depression as listed in the American Psychiatric Association's *Diagnostic and Statistical Manual of Mental Disorders, 4th Edition* (APA 1994). Patients are asked to consider each statement as it relates to the way they have felt for the past 7 days. There is a 4-point scale for each item ranging from 0 to 3. The 16 items corresponding to 9 depression domains are summed to give a single score ranging from 0 to 27, with higher scores denoting greater symptom severity. The domains assessed by the instrument include sad mood, concentration, self-criticism, suicidal ideation, interest, energy/fatigue, sleep disturbance (initial, middle, and late insomnia or hypersomnia), decrease/increase in appetite/weight, and psychomotor agitation/retardation. Additional information and the QIDS-SR₁₆ questions may be found on the University of Pittsburgh Epidemiology Data Center web site (Inventory of Depressive Symptomatology/Quick Inventory of Depressive Symptomatology [WWW]) (Rush et al. 2003; Trivedi et al. 2004).

9.4.7. Hepatic Safety Monitoring

If a study patient with ALT and AST within the normal range at baseline experiences elevated transaminases greater than 2x ULN, then a repeat measurement should be performed within 48 - 72 hours. If elevations greater than 2x ULN persist, then subjects should be evaluated for other causes of transaminase elevation and with additional tests of hepatic status. Close observation for suspected DILI will be conducted. If no other cause is found, then investigational product should be discontinued (see guidelines in Section 8.1).

If a study patient with ALT and AST above the normal range at baseline develops further elevations of ALT or AST >2x the baseline value or a bilirubin >2x ULN during the study, then repeat testing should be performed within 48 - 72 hours. If there are persistent elevations (ALT or AST >2x baseline or bilirubin >2x ULN), then close observation for suspected DILI will be conducted. If no other cause is found, then discontinuation of investigational product should be considered (see guidelines in Section 8.1).

The decision to discontinue or temporarily interrupt investigational product should be considered based on factors that include how much higher than baseline ALT and AST were relative to the upper limit of normal (ULN) and how much the on-study ALT and AST levels have increased relative to baseline, in addition to whether there is concomitant elevation of bilirubin or INR (see guidelines in Section 8.1).

If the patient lives in a remote area, repeat laboratory testing and close monitoring can be performed locally and the results should be promptly communicated to the investigator.

Close Observation for Suspected DILI

- Repeat liver enzyme and serum bilirubin tests two or three times weekly. Frequency of repeat testing can decrease to once a week or less if abnormalities stabilize or the trial drug has been discontinued and the subject is asymptomatic.
- Obtain a more detailed history of symptoms and prior or concurrent diseases.

- Obtain a history of concomitant drug use (including nonprescription medications and herbal and dietary supplement preparations), alcohol use, recreational drug use, and special diets.
- Rule out acute viral hepatitis types A, B, C, D, and E; autoimmune or alcoholic hepatitis; NASH; hypoxic/ischemic hepatopathy; and biliary tract disease.
- Obtain a history of exposure to environmental chemical agents.
- Obtain additional tests to evaluate liver function, as appropriate (e.g., INR, direct bilirubin).

Follow up testing may include ALT, AST, ALP, TBL, direct bilirubin, gamma-glutamyl transferase, and creatine phosphokinase to confirm the abnormality and to determine if it is increasing or decreasing. If the abnormality persists or worsens, clinical and laboratory monitoring should be initiated by the investigator and in consultation with the study medical monitor. Monitoring of ALT, AST, TBL, and ALP should continue until levels normalize or return to approximate baseline levels.

Hepatic Safety Data Collection

Additional safety data should be collected via the eCRF if 1 or more of the following conditions occur:

- Elevation of serum ALT to ≥ 5 x ULN for patients with normal/near-normal baseline ALT or to ≥ 5 x baseline value for patients with baseline ALT > 1.5 x ULN on 2 or more consecutive blood tests
- Elevated serum TBL to ≥ 2 x ULN
- Elevation of serum ALP to ≥ 2 x baseline value on 2 or more consecutive blood tests
- Patient discontinued from treatment due to a hepatic event or abnormality of liver tests
- Hepatic event considered to be a SAE.

9.4.8. Safety Monitoring

Lilly will periodically review evolving aggregate safety data within the study by appropriate methods.

The Lilly designated medical monitor will monitor safety data throughout the course of the study. Lilly will review SAEs within time frames mandated by company procedures. The Lilly designated medical monitor will, as is appropriate, consult with the functionally independent Global Patient Safety therapeutic area physician or clinical scientist and periodically review trends in safety data and laboratory analytes. Any concerning trends in frequency or severity noted by an investigator and/or Lilly (or designee) may require further evaluation.

All deaths and SAE reports will be reviewed in a blinded manner by Lilly during the clinical trial. These reports will be reviewed to ensure completeness and accuracy, but will not be unblinded to Lilly during the clinical study. If a death or a clinical AE is deemed serious, unexpected, and possibly related to investigational product, only Lilly Global Patient Safety will be unblinded for regulatory reporting and safety monitoring purposes. These measures will

preserve the integrity of the data collected during this trial and minimize any potential for bias while providing for appropriate safety monitoring.

Investigators will monitor vital signs and carefully review findings that may be associated with cardiovascular events. Adverse event reports and vital signs will be collected at each study visit.

The cardiovascular monitoring plan includes the following:

- Regular monitoring of lipid levels
- Potential MACE (cardiovascular death, myocardial infarction, and stroke), other cardiovascular events (such as hospitalization for unstable angina, hospitalization for heart failure, serious arrhythmia, resuscitated sudden death, cardiogenic shock, and coronary interventions), and noncardiovascular deaths will be identified by the investigative site or through medical review and will be sent to a blinded Clinical Event Committee for adjudication at regular intervals.

9.4.8.1. Venous Thromboembolic Event Assessment

If a patient develops the signs and symptoms of a DVT or PE, appropriate local laboratory tests and imaging should be performed, as necessary, for diagnosis of the event. For confirmed cases, additional laboratory testing is recommended as outlined in [Appendix 5](#). All suspected DVT or PE will be independently adjudicated by a blinded Clinical Event Committee.

9.4.8.2. Data Monitoring Committee

A DMC will oversee the conduct of this study. The DMC will consist of members external to Lilly. This DMC will be guided by the DMC charter. At a minimum the DMC will include the following who have previous DMC experience:

- a specialist with expertise in hepatology and
- a statistician.

The DMC will review and evaluate data from the 12 week treatment period from patients in Cohort A.

In addition, the DMC may be convened if 2 or more patients permanently discontinue due to safety. The DMC chair will determine if the full DMC needs to convene.

The DMC chair will have access to all SAEs as reported to regulatory authorities and may convene a meeting at any time.

Access to the unblinded interim data will be limited to the statisticians who conduct the interim analyses and the DMC. The statisticians conducting the interim analyses will be independent from the study team. The study team will not have access to the unblinded data.

Data that the DMC will review include, but are not limited to, reasons for study discontinuation, AEs including SAEs, clinical laboratory data and vital signs. The DMC may recommend continuation of the study as designed, temporary suspension of enrollment, or discontinuation of a particular dose regimen or discontinuation of the entire study. The DMC may request to review efficacy data to investigate the benefit/risk relationship in the context of safety

observations for ongoing patients in the study. Details of the DMC and interim safety analyses will be documented in a DMC charter.

In addition to the DMC members, a limited number of prespecified individuals may gain access to the unblinded PK, safety, and efficacy data (as specified in the unblinding plan) prior to the final database lock to initiate the exploration and/or final population of the PK/PD model development processes. Information that may unblind the study during the analyses will not be reported to study sites or the blinded study team until the database is locked.

9.5. Pharmacokinetics

[Redacted]

[Redacted]

[Redacted]

[Redacted]

[Redacted]

[Redacted]

[Redacted]

[Redacted]

[Redacted text block]

[Redacted text block]

[Redacted text block]

[Redacted text block]

9.6. Pharmacodynamics

[Redacted text block]

9.7. Biomarkers

Biomarker research is performed to address questions of relevance to drug disposition, target

[Redacted text block]

[Redacted text block]

[Redacted text block]

[Redacted text block]

[Redacted text block]

10. Statistical Considerations

10.1. Sample Size Determination

Approximately 20 patients will be randomized to the baricitinib 2-mg and placebo treatment groups for Cohort A. Twelve patients will be randomly assigned to the 2-mg treatment group and 8 patients to the placebo treatment group. This sample size is appropriate to provide sufficient preliminary safety and tolerability information for baricitinib 2-mg dose in patients with PBC prior to studying 4-mg baricitinib.

For Cohort B, 32 patients will be randomized to the baricitinib 4-mg and placebo treatment groups. Twenty patients will be randomized to the baricitinib 4-mg treatment group and 12 patients to placebo.

Overall, 20 patients per group will be assigned to the baricitinib 4-mg and placebo dose groups. Based on this sample size, this study will have approximately 81% power to detect a difference in ALP change from baseline between baricitinib 4-mg and placebo at Week 12 assuming that the true difference is 65 U/L. The sample size was determined based on a 2-sample t-test with 2-sided alpha level of 0.1 and a standard deviation of 80 U/L for the change from baseline in ALP. The sample size calculation was performed using nQuery® Advisor 7.0 software.

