5.1. Overall Design

Study I4V-MC-JAIV (JAIV) is a multicenter, randomized, double-blind, parallel, placebo-controlled, proof-of-concept Phase II study in patients with primary biliary cholangitis (PBC) who have an inadequate response or are intolerant to UDCA that will be conducted in 2 cohorts. Both cohorts will follow the same study schedule.

Cohort A

Cohort A is a randomized, double-blind, parallel, placebo-controlled cohort comprised of the first group of patients. At least twelve patients will be randomized to baricitinib 2-mg and at least eight patients will be randomized to placebo. Once Cohort A has fully enrolled, enrollment will be suspended.

Once all Cohort A patients have completed the 12 week treatment period their data will be reviewed by an external DMC.

The primary goal of Cohort A will be to assess the tolerability and safety of baricitinib 2-mg compared to placebo through Week 12. Efficacy measures, such as change in ALP will also be assessed to provide context for the benefit:risk ratio.

A DMC will oversee this study (Section 9.4.8.2).

Cohort B

Cohort B is a randomized, double-blind, parallel, placebo-controlled phase comprised of the second group of patients. At least twenty patients will be randomized to baricitinib 4-mg and at least twelve patients will be randomized to placebo.

Enrollment in Cohort B will begin only after the DMC review of Cohort A is complete and Lilly has received and accepted a recommendation to proceed.

Figure JAIV.1 illustrates the study design.

All procedures to be conducted during the study, including timing of all procedures, are indicated in the Schedule of Activities (Section 2). Section 7.6 describes permitted concomitant therapy. Study governance considerations are described in detail in Appendix 3.

Each cohort of the study consists of 3 periods:

Screening Period: The screening period is up to 49 days and begins when the patient signs the informed consent form (ICF). In exceptional circumstances, the screening window can be extended after consultation with the sponsor where local authorities permit. During the screening period, the investigator must confirm the patient meets all inclusion and no exclusion criteria for the study (Section 6). Two assessments of AST, ALT, ALP, and total bilirubin values are required prior to randomization (by at least two measurements obtained at least 4 weeks apart). If the AST, ALT, ALP, or bilirubin values from the second sample are increased more

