5.2. Determination of Sample Size

Approximately 20 patients will be randomized to the baricitinib 2-mg and placebo treatment groups for Cohort A. Twelve patients will be randomly assigned to the 2-mg treatment group and 8 patients to the placebo treatment group. This sample size is appropriate to provide

sufficient preliminary safety and tolerability information for baricitinib 2-mg in patients with PBC prior to studying 4-mg baricitinib.

For Cohort B, 32 patients will be randomized to the baricitinib 4-mg and placebo treatment groups. Twenty patients will be randomized to the baricitinib 4-mg treatment group and 12 patients to placebo.

Overall, 20 patients per group will be assigned to the baricitinib 4-mg (Cohort B) and placebo (Cohorts A and B) dose groups. Based on this sample size, this study will have approximately 81% power to detect a difference in ALP change from baseline between baricitinib 4-mg and placebo at Week 12 assuming that the true difference is 65 U/L. The sample size was determined based on a 2-sample t-test with 2-sided alpha level of 0.1 and a standard deviation of 80 U/L for the change from baseline in ALP. The sample size calculation was performed using nQuery[®] Advisor 7.0 software.

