6.1.3. Analysis Methods

The primary analysis for all continuous efficacy and health outcome variables will use a mixed-effects models for repeated measures (MMRM) with [REDACTED]

[REDACTED] An unstructured covariance matrix will be used to model the within-patient variance-covariance errors. If the unstructured covariance matrix results in a lack of convergence, the heterogeneous Toeplitz covariance structure, followed by the heterogeneous autoregressive covariance structure will be used. The Kenward-Roger method will be used to estimate the denominator degrees of freedom. Type III tests will be used for all the statistical comparisons; the 90% confidence interval (CI) will also be reported. The LS mean difference, standard error, p-value, and CI will also be reported. Treatment group comparisons at specific study visits will be tested using the t-test obtained from the MMRM results. Data will be censored as described in Section 6.3.

The primary analysis for all categorical efficacy and health outcome variables will use a logistic regression analysis [REDACTED]

[REDACTED] The p-value and 90% (unless otherwise specified) CI for the odds ratio from the logistic regression model will be used for primary statistical inference. When logistic regression sample size requirements are not met, (<5 responders in any category for any factor), the p-value from the Cochran-Mantel-Haenszel (CMH) test with [REDACTED]

In addition, all primary and secondary continuous efficacy and health outcome variables will use analysis of covariance (ANCOVA) models [REDACTED]

[REDACTED] and cohort in the model as a supplementary analysis. Type III sums of squares for the least-squares mean (LSM) will be used for the statistical comparison of treatment groups, and the LSM difference, standard error, p-value and 90% CI will also be reported. The last observation carried forward (LOCF) approach will be used to impute missing data.

All safety data will be descriptively summarized by treatment groups and analyzed using the safety population.

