6.2. Covariate Adjustment

The randomization to treatment groups at Week 0 (Visit 3) is stratified by [REDACTED]

The covariates used in the ANCOVA model for continuous data generally will include the parameter value at baseline. Inclusion of baseline in the ANCOVA model ensures that treatment LSMs are estimated at the same baseline value. When an MMRM analysis is performed, baseline value and baseline-by-visit interactions will be included as covariates.

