6.10.3. Supplementary Analyses

Supplementary analyses for select outcomes have been previously described and include the following:

- Non-responder imputation (NRI) (Section 6.3.3) for categorical secondary outcomes.
- Analysis of continuous outcomes with ANCOVA (Section 6.1.3), with missing data imputed using LOCF (Section 6.3.1) for continuous primary and secondary outcomes.

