6.14. Subgroup Analyses

Subgroup analyses comparing each dose of baricitinib to placebo will be performed on the mITT population at Week 12, with data up to rescue for the following:

- Change from baseline in alkaline phosphatase (ALP) at Week 12.

The following subgroups (but not necessarily limited to only these) will be evaluated:

- 

Descriptive statistics will be provided for each treatment and stratum of a subgroup as outlined, regardless of sample size. The analysis will be performed using MMRM. The model will include treatment, subgroup, and treatment-by-subgroup interaction as explanatory variables. The treatment-by-subgroup interaction comparing treatment groups will be tested at the 0.1 significance level. The p-value from the MMRM will be reported for the interaction test. Response counts and percentages will be summarized by treatment for each subgroup category. Type III tests will be used for all the statistical comparisons; the 90% confidence interval (CI) will also be reported. The LS mean difference, standard error, p-value, and CI will also be reported. Treatment group comparisons at specific study visits will be tested using the t-test obtained from the MMRM results. Additionally, descriptive statistics will also be provided for each treatment and cohort (Cohort A and Cohort B) as a subgroup.

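### Is the 81% power for 4 mg against placebo wrong because 8 of the 20 placebo patients come from the earlier cohort?

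*Protocol*

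**What the plan says.** Protocol 10.1 gives the power statement: "this study will have approximately 81% power to detect a difference in ALP change from baseline between baricitinib 4-mg and placebo at Week 12". The difference taken as true is 65 U/L. The method is a two-sample t-test with two-sided alpha 0.1 and an SD of 80 U/L. The same section gives the allocation: 12 on 2 mg and 8 on placebo in Cohort A, 20 on 4 mg and 12 on placebo in Cohort B.

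SAP 5.2 repeats the calculation and says where the groups come from: "Overall, 20 patients per group will be assigned to the baricitinib 4-mg (Cohort B) and placebo (Cohorts A and B) dose groups".

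The cohorts run in sequence. Under protocol 5.1, "Once Cohort A has fully enrolled, enrollment will be suspended", and Cohort B opens only after the DMC review is complete and the sponsor has accepted a recommendation to proceed.

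On the analysis of ALP change:

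- The list of terms in the primary MMRM is redacted in protocol 10.3.1.1 and SAP 6.1.3. SAP 6.2 adds: "When an MMRM analysis is performed, baseline value and baseline-by-visit interactions will be included as covariates".
- SAP 6.1.3 also describes an ANCOVA with some redacted terms "and cohort in the model as a supplementary analysis". SAP 6.10.3 lists it again: "Analysis of continuous outcomes with ANCOVA (Section 6.1.3), with missing data imputed using LOCF (Section 6.3.1) for continuous primary and secondary outcomes".
- SAP 6.14 says that "descriptive statistics will also be provided for each treatment and cohort (Cohort A and Cohort B) as a subgroup".

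**The concern.** The 4 mg dose is randomised only in Cohort B, so 8 of its 20 controls (40%) were enrolled before any patient could receive that dose. Counting them at full weight is valid only if mean placebo change in ALP is the same in both cohorts. The readable text never states that condition.

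The plan also treats cohort as a possible adjustment factor: it is in the supplementary ANCOVA of ALP and in the logistic model for categorical outcomes. With treatment and cohort both in a single-timepoint model, each of the four treatment-by-cohort groups has its own mean, and Cohort A placebo drops out of the 4 mg contrast.

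At stake is how to read the only power figure given for the primary comparison. If the primary model fits cohort, the figure may be too high. If it does not, a difference between the cohorts' placebo responses would pass into the estimate.

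**Working it through.** **Inputs from the plan** (protocol 10.1, SAP 5.2): difference 65 U/L, SD 80 U/L, two-sided alpha 0.1; group sizes 8 (A placebo), 12 (A 2 mg), 12 (B placebo), 20 (B 4 mg).

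**Method.** SE = 80 × √v, where v is the sum of the reciprocal group sizes. The noncentrality is 65/SE. Power is the noncentral t probability beyond the two-sided 10% critical values.

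**1. The plan's own figure.** v = 1/20 + 1/20 = 0.1000; SE = 80 × √0.1000 = 25.3 U/L; noncentrality = 65/25.3 = 2.57; 38 df. Power = 81.0%. The stated figure is reproduced.

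**2. Cohort fitted at one timepoint.** Least squares with intercept, cohort, 2 mg and 4 mg gives the 4 mg contrast these weights on the group means: B 4 mg +1, B placebo −1, A placebo 0, A 2 mg 0. So v = 1/20 + 1/12 = 0.1333; SE = 80 × √0.1333 = 29.2 U/L; noncentrality = 65/29.2 = 2.23.

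- Power is 70.2% with 30 df (Cohort B only) and 70.8% with 48 df (residual variance from all 52 patients, four parameters).
- Reaching 81.0% here takes a true difference of 75.4 U/L (30 df) or 74.8 U/L (48 df).

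**3. Baseline adjustment, both comparisons treated alike.** The 80 U/L is the SD of the change score. With equal variances s² at baseline and Week 12 and correlation r, the change has variance 2s²(1 − r), and after adjustment for baseline s²(1 − r²). The ratio is (1 + r)/2. The documents do not give r, so a range is assumed.

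| Assumed r | Factor (1 + r)/2 | Pooled 20 vs 20 (48 df) | Cohort fitted, 20 vs 12 (47 df) |
|---|---|---|---|
| 0.5 | 0.75 | 90.0% | 81.3% |
| 0.9 | 0.95 | 83.0% | 72.7% |

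The gap is 8.7 points at r = 0.5 (90.0 − 81.3) and 10.3 points at r = 0.9 (83.0 − 72.7). Over this range the pooled comparison is above 81% throughout. The 20 against 12 comparison reaches 81% only if r is about 0.51 or lower.

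**4. If the MMRM contained cohort** (assumed: complete data, compound symmetry, four post-baseline visits, no baseline adjustment, 48 df). A cohort effect that varies by visit gives v = 0.1333 and 70.8%. A constant cohort effect lets Cohort A placebo contribute something: v = 0.1158 and 76.1% at a within-patient correlation of 0.3, v = 0.1308 and 71.6% at 0.9.

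**5. If the MMRM omits cohort and the placebo means differ by D.** The 4 mg estimate shifts by (8/20) × D = 0.4D. For an illustrative D of 20 U/L the shift is 8 U/L. Power at a true 65 U/L becomes 71.5% or 88.3% depending on direction, and the two-sided false-positive rate rises from 10% to 11.6% (38 df, SD held at 80). The documents give no value for D.

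**The case for a change.** The strongest case for a change is that disclosing where the controls come from is not the same as stating the condition that makes pooling valid. Protocol 10.1 does not itself say that the 20 are pooled over cohorts; only SAP 5.2 does. Baseline adjustment does not remove the issue, because it raises both figures and leaves a gap of about 9 to 10 points. A reader who uses the cohort-adjusted ANCOVA to support the primary result is not told that its 4 mg contrast rests on 12 controls. One or two sentences would put this right at no cost in patients or analyses.

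Much of this stands. The zero weight is algebra, and the gap is real wherever cohort is fitted. But the condition can be read from what is written: a two-sample t-test with one difference and one SD already implies a single placebo mean. Protocol 10.1 gives 8 and 12 placebo patients and then 20 overall, so the sum is visible within the section. Both cohorts share one schedule and one set of entry criteria, which makes equal placebo response plausible, though not certain. The design rationale in protocol 5.4 is redacted and may discuss pooling. Finally, a supplementary analysis does not need its own power statement.

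**Conclusion.** No change follows. The 81% is right for the test and group sizes it names, and the documents show where the 20 placebo patients come from. The figure of about 70% belongs to a single-timepoint model with cohort and without baseline adjustment. That is not known to be the primary analysis, because the MMRM terms are redacted, and it leaves out the baseline covariate that SAP 6.2 plans. With baseline in both comparisons, at an assumed r of 0.5 to 0.9 and equal variances, the figures are 90.0% to 83.0% pooled and 81.3% to 72.7% with cohort fitted. No failure of the stated figure is shown.

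What remains is an unwritten assumption: equal mean placebo change in the two cohorts. Writing it down would be tidy, but it would change no sample size, model, result or decision. The two outputs that would reveal a cohort difference, the cohort-adjusted ANCOVA and the by-cohort ALP descriptives, are already planned. An analyst can read them beside the primary result without any amendment. This would need another look only if the unredacted primary model turned out to contain cohort, since the 81% would then describe a different comparison from the one fitted.
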